### • Composite elevations:

- ALT or AST > 3 x ULN and TBL > 1.5 x ULN
- $\circ$  ALT or AST > 3 x ULN and TBL > 2 x ULN
- o ALT or ALT > 3 x ULN concurrent with TBL > 2 x ULN with exact Clopper-Pearson 95% CIs. Concurrent is defined as elevations on the same laboratory test collection date.
- o ALT or ALT > 3 x ULN concurrent with TBL > 2 x ULN and ALP ≤ 2 x ULN with exact Clopper-Pearson 95% CIs. Concurrent is defined as elevations on the same laboratory test collection date.
- o ALT or AST > 3 x ULN concurrent with AEs of interest: nausea, vomiting, anorexia, abdominal pain, and fatigue. For a given analysis period, an LFT elevation is concurrent with an AE of interest if the imputed AE start date is +/- 7 days inclusive of the LFT collection date; both the LFT collection date and the imputed AE start date must also be in the analysis period. The following PTs will be used to identify the AEs of interest: nausea, vomiting, anorexia, fatigue, and those containing "abdominal pain."

Subjects must have non-missing on-study LFT data (i.e., ALT, AST, TBL, or ALP) to be included.

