8.1.5 Potential Drug Induced Liver Injury (DILI)

Wherever possible, timely confirmation of the initial liver-related laboratory abnormalities should occur prior to the reporting of a potential DILI event. All occurrences of potential DILIs, meeting the defined criteria, must be reported as SAEs as per Section 8.1.2.

Potential drug induced liver injury is defined as:

1. Aminotransferases (AT) (ALT or AST) elevation > 3 times the upper limit of normal (ULN)

AND

2. Total bilirubin (TBL) > 2 times ULN, without initial findings of cholestasis (elevated serum alkaline phosphatase)

AND

3. No other immediately apparent possible causes of AT elevation and hyperbilirubinemia, including but not limited to, viral hepatitis, pre-existing chronic or acute liver disease, or the administration of other drug(s) known to be hepatotoxic.

If any potential DILI is identified and meets the criteria above, the Biohaven Medical Monitor (or designee) should immediately be contacted for further instruction on dosing adjustments and whether the subject must discontinue from the trial and appropriate follow up requirements.

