### **eDISH Scatter Plot**

An evaluation of drug-induced serious hepatotoxicity (eDISH) scatter plot will display the maximum TBL ratio of value to ULN on the y-axis versus the maximum ALT ratio of value to ULN on the x-axis by treatment group (excluding All BHV-3500), where both maxima will be on treatment but not necessarily concurrent. Both axes will be on the  $\log_{10}$  scale. Ratios < 0.1 x ULN will be set to 0.1. Sample sizes in the legend will represent subjects with paired ratios. A horizontal reference line will be placed at 2 x ULN, and a vertical reference line will be placed at 3 x ULN. The lower left quadrant will be labeled "Normal Range", the upper left quadrant will be labeled "Hyperbilirubinemia", the lower right quadrant will be labeled "Temple's Corollary", and the upper right quadrant will be labeled "Possible Hy's Law Range."

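### Two liver-test rows in SAP 6.5.2.2 name ALT twice where ALT or AST is evidently meant, so read literally they and their confidence intervals omit a same-date case driven by AST alone (minor)

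*SAP*

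**What the plan says.** SAP 6.5.2.2 lists five composite elevations, tabulated for treated subjects separately in the pre-treatment and on-treatment periods.

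- Two rows combine an aminotransferase with total bilirubin without any timing condition, at bilirubin thresholds of 1.5 x and 2 x ULN. The second reads "ALT or AST > 3 x ULN and TBL > 2 x ULN".
- Two rows add a timing condition. The first is "ALT or ALT > 3 x ULN concurrent with TBL > 2 x ULN", with exact 95% intervals. The second is "ALT or ALT > 3 x ULN concurrent with TBL > 2 x ULN and ALP ≤ 2 x ULN", also with exact intervals. For both, "Concurrent is defined as elevations on the same laboratory test collection date".
- The last row pairs liver tests with symptoms: "ALT or AST > 3 x ULN concurrent with AEs of interest".

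The two same-date rows are the only composite rows with a confidence interval, and the only ones that do not name AST.

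The first criterion for potential drug-induced liver injury in Protocol 8.1.5 is "Aminotransferases (AT) (ALT or AST) elevation > 3 times the upper limit of normal (ULN". It is joined to total bilirubin above 2 x ULN without initial cholestasis and to the absence of another apparent cause. The trigger for the by-subject LFT listing (SAP 6.5.2) and the trigger for safety narratives (SAP 6.5.7) also name both enzymes.

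**The concern.** A condition satisfied by ALT or by ALT is simply a condition on ALT. Because the wording occurs in both rows, a programmer working from the SAP could implement it faithfully and leave AST out of both.

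The table would then contradict itself. Take a subject with AST above 3 x ULN, ALT not above 3 x ULN and bilirubin above 2 x ULN on one date. That subject counts in the row without a timing condition and not in the same-date rows. A reader would naturally conclude that the two elevations fell on different dates, which would be false.

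The row with the ALP limit is also the only composite row with any condition on ALP, and so the one that comes nearest to the no-cholestasis part of Protocol 8.1.5. It too would show no case.

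**Working it through.** The plan states no count, rate or power for these rows, so there is no figure to reproduce. The check has two parts: how the rows classify a case, and what one misclassified case does to the interval.

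**1. Classification.** Test values are multiples of ULN, chosen to represent each pattern, with ALP at 1.

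| Pattern | ALT | AST | TBL | Same date | Non-concurrent row, TBL > 2 | Both same-date rows, as written | Both same-date rows, with ALT or AST |
|---|---|---|---|---|---|---|---|
| ALT only | 4 | 1 | 2.5 | yes | counted | counted | counted |
| Both enzymes | 4 | 4 | 2.5 | yes | counted | counted | counted |
| AST only | 1 | 4 | 2.5 | yes | counted | **not counted** | counted |
| AST only | 1 | 4 | 2.5 | no | counted | not counted | not counted |

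Only the third pattern changes. Any case with ALT above 3 x ULN is treated the same under either wording.

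**2. Effect on the interval.** Inputs:

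- Group size: about 380, the projected mITT number per group in SAP section 5 (95% of 400). This is an assumption. The table uses treated subjects with liver-test data, whose number is not projected.
- Pooled active group: 3 x 380 = 1140. SAP sections 6 and 6.5 include an All BHV-3500 column in the safety tables.
- Number of AST-only same-date cases: one, assumed. The documents give no expected frequency.

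Exact (Clopper-Pearson) 95% upper limits:

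- For 0 of N, the limit is 1 - 0.025^(1/N).
- For 1 of N, the limit is the p that solves (1 - p)^N + N p (1 - p)^(N-1) = 0.025.

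Results:

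| N | Shown as written | Upper limit | Shown when corrected | Upper limit |
|---|---|---|---|---|
| 380 | 0/380 | 1 - 0.025^(1/380) = 0.97% | 1/380 = 0.26% | 1.46% |
| 1140 | 0/1140 | 1 - 0.025^(1/1140) = 0.32% | 1/1140 = 0.09% | 0.49% |

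Relative change in the upper limit: (1.457 - 0.966) / 1.457 = 34% at N = 380, and (0.488 - 0.323) / 0.488 = 34% at N = 1140.

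Sensitivity to the assumed size: at 360 per group the two limits are 1.02% and 1.54%, and at 400 per group they are 0.92% and 1.39%. The assumption about N matters little. The assumption that one such case occurs decides whether there is any effect at all.

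**3. Where the AST-only case still appears.**

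- SAP 6.5.2.2: both non-concurrent composite rows, the cumulative and mutually exclusive rows for AST, for ALT or AST and for bilirubin, and the AST shift table.
- SAP 6.5.2: the by-subject LFT listing.
- SAP 6.5.7: the narrative listing.
- Protocol 8.1.5: reporting as a serious adverse event, if the full definition of potential liver injury is met.

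**The case against.** The strongest reply is that this is a typing slip with an obvious meaning. Nobody would deliberately specify the same enzyme twice, every neighbouring combined row shows what was intended, and the table templates are in a separate mock document (SAP 7.1.1) that may already be right. This is fair as to intent. It does not correct the operative definition, and whether the programs follow the SAP literally cannot be seen from these documents.

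A second reply is that the design makes the loss small. Protocol Table 1 schedules one post-dose laboratory draw, at the End of Treatment Visit. With a single draw, the non-concurrent row with the same thresholds gives the count that a corrected first same-date row should give, and anyone can compute an exact interval from it. This largely stands. The two can separate only if there are further draws, which is possible because Protocol 8.1.5 asks for confirmation of liver abnormalities where feasible. The non-concurrent row also does not replace the row with the ALP limit.

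Three stronger readings are tempting, and the documents do not support them.

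- A reader might infer that these rows are the trial's main liver-safety signal. Neither document ranks them above the other rows or labels them as Hy's law; only a quadrant of the eDISH plot carries that label.
- A reader might infer that an AST-only case would be lost, or be visible in one row only. The places listed in the working rule this out.
- A reader might treat the eDISH plot, which puts "the maximum ALT ratio of value to ULN on the x-axis", as the same error. It is a separate and explicit choice, and correcting the two rows would not alter it.

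Nor does Protocol 8.1.5 state a same-date requirement. The conflict with it concerns which aminotransferases qualify. It does not show that these two rows were meant to reproduce the protocol definition.

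**Conclusion.** The two rows are wrong as written, and the severity is minor. Read literally, they exclude a same-date case driven by AST alone, and so disagree with the adjacent non-concurrent row and with the aminotransferase criterion in the protocol. The consequence is confined to two summary counts and their exact intervals. Identification and reporting of the individual case do not depend on them, and no efficacy result is touched.

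The numerical effect is conditional. With one such case, the row would show none instead of one, and its upper limit would be about a third too low, both per group and pooled. With no such case, nothing changes. This rests on the assumed single case, on the mITT projection standing in for treated subjects with liver tests, and on the programs following the SAP text.

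**What to change.** In SAP 6.5.2.2, replace the second ALT with AST in both same-date composite rows, so that each names ALT or AST like the other composite rows. Check that the mock tables, the analysis dataset derivations and the table programs use both enzymes.

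The cost is one word in each of two rows, plus that check. No data collection, sample size or error-control provision changes, and cases with ALT above 3 x ULN are counted as before.

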4 STUDY PLAN

4.1 Study Design and Duration

This is a double-blind, randomized, multicenter, outpatient evaluation of the safety and efficacy of BHV-3500 as compared to placebo in the treatment of moderate or severe migraine. Subjects will be dispensed one Aptar Unit Dose System (UDS) liquid spray device containing a single dose of study medication BHV-3500 or a matching placebo. The total duration of the study will be approximately 11 weeks. This includes a 3-28 day Screening Period, a Treatment Phase that can last up to 45 days or until the subject has a migraine that reaches moderate or severe intensity, followed by an End of Treatment Visit 7 (+2) days after the administration of study medication.

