4.2 Study Schematic

4.3 Schedule of Assessments

Table 1: Schedule of Assessments

Procedure	Screening Visit ¹	Baseline/ Randomization Visit (Day 1) ²	Onset of moderate or severe migraine ³	Post Study Medication Administration: 15, 30, 45, 60 and 90 minutes 2, 3, 4, 6, 8, 24 and 48 hours	End of Treatment Visit ¹⁴
		Elig	ibility Assessments		
Informed Consent	X				
Inclusion/ Exclusion Criteria	X	X			
Medical History	X				
Migraine History Assessment (signs/ symptoms/ prior treatment/ frequency/ intensity)	X				
Rescue Medication paper diary, Concomitant Medication paper diary ⁴	X	X	X	X	X
Randomize subject in IWRS ⁵		X			
		Sa	fety Assessments		
Physical Examination	X				X
Nasal Inspection ⁶	X	X			X
Vital Signs/ Physical Measurements ⁷	X	X			X
Adverse Event and Serious Adverse Event Assessment ⁸	X	X	X	X	X
Sheehan Suicidality Tracking Scale (S-STS) ⁹	X	X			X
ECG	X				X
Clinical Safety Laboratory Testing	X				X

		Baseline/ Randomization Visit	Onset of moderate or	Post Study Medication Administration: 15, 30, 45, 60 and 90 minutes	End of Treatment
Procedure	Screening Visit ¹	$(Day 1)^2$	severe migraine ³	2, 3, 4, 6, 8, 24 and 48 hours	Visit ¹⁴
Liver Function Tests (LFTs)					X
Lipid Panel	X				
FSH, if applicable, to determine WOCBP status	X				
Pregnancy Test ¹⁰	X (Serum)	X (Urine)	X (Urine)		X (Serum)
Urinalysis	X				X
Urine drug screen for drugs of abuse	X				X
		Clinical Dru	ig Supplies/Study Supplie	s	
eCOA Handheld device assigned		X			
Dispense study medication ¹¹		X			
Administer study medication			X		
Patient Education: Dose Administration		X			
Patient Education: eCOA Handheld		X			
Enter use of study medication in eCOA Handheld device			X		
Return used or unused study medication					X
eCOA Handheld returned/ reviewed for completeness ¹²					X

Procedure	Screening Visit ¹	Baseline/ Randomization Visit (Day 1) ²	Onset of moderate or severe migraine ³	Post Study Medication Administration: 15, 30, 45, 60 and 90 minutes 2, 3, 4, 6, 8, 24 and 48 hours	End of Treatment Visit ¹⁴
Efficacy Assessments ¹²					
Assessment of migraine pain ¹³			X	X	
Assessment of Migraine Symptoms (photophobia, phonophobia, and nausea) ¹³			X	X	
Functional Disability Scale ¹³			X	X	
MQoL (Migraine Quality of Life Questionnaire) ¹³				X (24-hour assessment)	
Preference of Medication (PoM) ¹³				X (24-hour assessment)	

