4.3.4 End of Treatment Visit

Subjects will return to the site for their End of Treatment Visit (after assessments in the handheld are completed) within 7 (+2) days after dosing with study medication. The "+2" day window is included for scheduling purposes only.

At the End of Treatment Visit, medication compliance, monitoring of tolerability and safety assessments (including vital signs, laboratory tests, nasal inspection and electrocardiography) will be performed. Refer to Table 1 for a full list of assessments completed at the EOT.

If a subject has NOT experienced a migraine headache of moderate or severe intensity within 45 days after randomization, they are still required to complete all EOT visit procedures. All subjects must return used and unused study medication and their handheld device to the investigational site.

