## 7.4 Analysis Periods

Analysis periods are defined as follows:

- Pre-treatment: measurement date/time at or before the study drug start date/time. This period is used to derive baseline values and to assess pre-treatment endpoints.
- On-treatment: measurement date/time after the study drug start date/time. Note that AEs with imputed start date equal to the study drug start date are part of this period.
- On-study: measurement date/time after the randomization date/time.

See Section 7.3 for derived dates for determining analysis periods.

If measurement time is missing or not collected for a parameter, then the measurement date will be compared to the derived date.

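### The SAP pairs liver enzyme elevations with symptoms by AE start date only, within 7 days, so with a protocol-compliant blood draw on day 8 or 9 a dosing-day symptom is scored not concurrent even if still present

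*SAP*

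**What the plan says.** SAP 6.5.2.2, under composite elevations, includes a row for ALT or AST above 3 x ULN together with nausea, vomiting, anorexia, abdominal pain or fatigue. The elevation is "concurrent with an AE of interest if the imputed AE start date is +/- 7 days inclusive of the LFT collection date", with the further condition that "both the LFT collection date and the imputed AE start date must also be in the analysis period". The rule mentions neither the AE stop date nor whether the AE is ongoing.

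The timing of the liver test comes from the protocol. Table 1 schedules liver function tests after dosing only at End of Treatment; the general safety laboratory panel is marked only at Screening and End of Treatment. Protocol 4.1 places the "End of Treatment Visit 7 (+2) days after the administration of study medication". Protocol 4.3.4 and Table 1 footnote 14 put it "within 7 (+2) days after dosing with study medication" and add that the +2 "day window is included for scheduling purposes only". SAP 2.1 has subjects return within 7 days of treatment and does not mention the +2.

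On the analysis side, SAP 7.4 states that AEs "with imputed start date equal to the study drug start date are part of this period", meaning the on-treatment period, so a dosing-day symptom is otherwise eligible for the row. SAP 7.5 defines the end of treatment window as anything after study drug start, without an upper limit.

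**The concern.** The row is the only tabulation in the SAP that links an aminotransferase elevation to these symptoms in the same subject. Its window is 7 days, while the protocol lets the relevant blood draw occur 9 days after the single dose. A visit that complies fully with the protocol can therefore put the dosing day out of reach.

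The clearest failure is a symptom that begins on the dosing day and is still present when blood is drawn on day 8 or 9. Symptom and elevation then exist on the same date, yet the rule calls them not concurrent because it looks only at when the symptom began. The screening sample cannot rescue the pair, since both dates must lie in the same analysis period.

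Start-date imputation can add to this. Under SAP 7.6.1.1 a wholly missing AE start date is set first to the date of study medication, and so is a partial date that is consistent with that date but whose earliest possible value precedes it. An AE imputed to the dosing day fails the test whenever the draw is on day 8 or later.

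Since few subjects are likely to exceed 3 x ULN after one dose (an expectation, not a figure in the documents), losing a single pair could change what the row shows.

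**Working it through.** The plan gives a rule here rather than a computed figure, so the check is date arithmetic.

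**Inputs.** Let day 0 be the study drug start date (treatment day 1 in SAP 7.5), L the day of the LFT and a the day of the imputed AE start.
- Rule (SAP 6.5.2.2): concurrent if |a − L| ≤ 7.
- Latest compliant draw (Protocol 4.1, 4.3.4): L = 7 + 2 = 9.
- Earliest on-treatment AE start (SAP 7.4): a = 0.

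**Result.** For AEs that start before the draw, the pair is lost when a < L − 7.

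| LFT day L | Gap to a dosing-day AE | AE start days not counted |
|---|---|---|
| 7 or earlier | 7 or less | none |
| 8 | 8 | 0 |
| 9 | 9 | 0, 1 |
| 10 (outside the visit window but still analysed) | 10 | 0, 1, 2 |

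This takes the 7-day limit with its endpoints included, the natural reading. If the limit were read as 7 days counting the LFT day itself (|a − L| ≤ 6), a day 7 draw would also lose a dosing-day AE.

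**Would a wider symmetric window do?** With ±8, a day 9 draw still misses a dosing-day start (9 > 8). ±9 is the smallest window covering days 7, 8 and 9. It would not cover a later visit and would still ignore whether the symptom is present at the draw.

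**Can the loss be sized?** Only by assuming two things the documents do not give: when these AEs start and when visits occur. Suppose a share p starts on day 0 and the rest is spread evenly over days 1 to 7. The share not counted is then p at L = 8 and p + (1 − p)/7 at L = 9.
- p = 0.5: 0.50 at day 8; 0.50 + 0.50/7 = 0.571 at day 9.
- p = 0.9: 0.90 at day 8; 0.90 + 0.10/7 = 0.914 at day 9.

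Averaging over assumed visit days:
- all visits by day 7: 0%;
- even over days 3 to 9: (0.50 + 0.571)/7 = 15% to (0.90 + 0.914)/7 = 26%;
- even over days 7 to 9: 1.071/3 = 36% to 1.814/3 = 60%;
- all on day 9: 57% to 91%.

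These results run from nothing to nearly everything, driven by the assumptions. They also count every AE at any gap as a pair that ought to be found, including one that resolved within an hour of dosing.

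**Check of an overlap rule.** With L = 9 the window is days 2 to 16. An AE from day 0 and ongoing overlaps it and is counted. An AE that starts and stops on day 0 does not overlap and is not counted. An AE from day 1 to day 2 overlaps on day 2 and is counted.

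**The case against.** The strongest reply is that the row has little weight and the gap may seldom arise. Protocol 4.3.4 and SAP 2.1 can both be read as allowing visits before day 7, once the 48-hour handheld assessments are complete, and the two extra days are there only for scheduling. If most visits fall by day 7, the rule works. For an AE that has resolved, whether 7 or 9 days still counts as concurrent is a matter of judgement, not an error.

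Other outputs also show the data. SAP 6.5.7 flags every treated subject with on-treatment AST or ALT above 3 x ULN for the narrative listing, whatever the symptoms. SAP 6.5.2 lists all LFT results over time for such subjects, SAP 6.5.1 lists all AEs, and the elevation stays in the cumulative, mutually exclusive and shift tables. An unscheduled local laboratory result, which SAP 6.5.2 allows into the analysis, could capture some pairs.

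All of this stands, and it limits the point. It does not answer the case of a symptom still present at a day 8 or 9 draw, where the stated rule gives the wrong classification on a visit the protocol permits.

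Three stronger readings are tempting. A reader might infer that a third or more of pairs will be lost; that depends on assumed onset and visit distributions, as the working shows. A reader might infer that the comparison between arms is biased; the trial is randomised and double-blind, and nothing in the documents suggests that visit timing differs by arm. A reader might infer that a liver signal would be hidden; the other outputs show the elevations and the AEs.

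**Conclusion.** The point holds as a defect in one definition. For a draw on day 8, an AE of interest that started on the dosing day is scored not concurrent; for a draw on day 9, so is one that started the day after dosing. This follows from the SAP wording and the protocol visit window without any distributional assumption. It is plainly wrong when the symptom is still present at the draw, and arguable when the symptom has resolved.

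The effect is a possible undercount in a single descriptive row. Its frequency cannot be derived from the documents: it is zero if visits occur on or before day 7 (endpoints included) and unknown otherwise. No hypothesis test, type I error statement or efficacy estimate is touched. The correction is still worth making, because a zero in this row could otherwise reflect the date of the visit and not the absence of symptomatic elevations.

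**What to change.** In SAP 6.5.2.2, define concurrency by overlap: an LFT elevation is concurrent with an AE of interest if the interval from the imputed AE start date to the AE stop date overlaps the LFT collection date ± 7 days. Treat a missing stop date as ongoing. Keep the requirement that the LFT date and the imputed AE start date fall in the same analysis period.

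Do not go further and count every AE of interest from dosing through 7 days after the LFT. SAP 7.5 has no upper limit on the end of treatment window, so that rule would call a long-resolved dosing-day AE concurrent with a very late blood draw.

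Separately, reconcile the return visit in SAP 2.1 with the 7 (+2) day window in Protocol 4.1 and 4.3.4, so that analysis rules are written against one agreed visit window.

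The cost is a change of SAP text and a small programming change. AE stop dates are already available (SAP 7.3 uses them for last contact date), but the SAP imputes stop dates only for medications (7.6.2.2), so a short convention for AE stop dates must be added. A few more pairs may be counted. No new data are needed.
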